### 5.3 Exclusion Criteria

Subjects who meet any of the following criteria cannot be enrolled:

1. History of severe infection within 4 weeks to dosing.
2. Signs and symptoms of any active infection regardless of severity within 2 weeks prior to dosing.
3. Meals & Dietary Restrictions: No seafood or high-fat food will be served during confinement in the clinical center
4. Subjects who have any history of allergy to food or drug will be excluded ( Including allergies, hypersensitivity, or intolerance to rice or rice products )
5. Use of any prescription drugs, herbal supplements, or nonprescription drugs including oral anti-histamines (for seasonal allergies) within 1 month or 5 half-lives (whichever is longer) prior to study drug administration, or dietary supplements within 1 week prior to study drug administration, unless, in the opinion of the Investigator and Sponsor, the medication will not interfere with the study. Over-the-counter multivitamins will be permitted. If needed, paracetamol/acetaminophen may be used, but must be documented in the Concomitant medications/Significant non-drug therapies page of the source data. Any questions of concomitant medications should be directed to the Sponsor.
6. Participation in a clinical research study involving the administration of an investigational or marketed drug or device within 30 days prior to the first dosing, administration of a biological product in the context of a clinical research study within 90 days prior to the first

dosing, or concomitant participation in an investigational study involving no drug or device administration.

7. Donation of blood 12 week prior to dosing.
8. Pregnant, or nursing females.
9. A history of substance abuse, psychiatric and psychological condition that, in the judgment of the investigator, may interfere with the planned treatment and follow-up, affect subject compliance or place the subject at high risk from treatment-related complications
10. A history of severe allergic reaction to any HpHSA component.
11. A marked baseline prolongation of QT/QTc interval (e.g., repeated demonstration of a QTcF interval >450 milliseconds [ms])
12. History of or active obstructive disease in biliary tract, liver, kidney and spleen defined by ultrasound
13. Subjects who test positive for hepatitis B or C. (no matter carriers or active will be excluded from the study)
14. Subjects who test positive for Syphilis, Human immunodeficiency virus (HIV) positive will also be excluded from the study
15. Immunization with a live or attenuated vaccine is prohibited within 4 weeks prior to study drug administration. Seasonal influenza vaccines for injection are generally killed virus vaccines and are allowed; however, intranasal influenza vaccines (e.g., FluMist®) are live attenuated vaccines and are not allowed)
16. Positive Ig E and Ig G against rice at screening
17. History of significant alcohol abuse within one year prior to screening or regular use of alcohol within six months prior to the screening visit (more than fourteen units of alcohol per week [1 unit = 150 mL of wine, 360 mL of beer, or 45 mL of 40% alcohol]) or positive alcohol breath test at screening
18. History of significant drug abuse within one year prior to screening or use of soft drugs (such as marijuana) within 3 months prior to the screening visit or hard drugs (such as cocaine, phencyclidine [PCP], crack, opioid derivatives including heroin, and amphetamine derivatives) within 1 year prior to screening
19. Positive urine drug screen, cotinine test, or alcohol breath test at screening
20. Any reason which, in the opinion of the Qualified Investigator, would prevent the subject from participating in the study.

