The development of screening has been greatly decreased the risk for transmission of blood-derived infectious pathogens, however, the risk has never been eliminated and is always there. To eliminate the potential risk of viral contamination, regulatory agencies in some have encouraged pharmaceutical companies to use non-animal-derived sources for pharmaceutical production (12). Thus, the development of a low-cost method for the production of recombinant HSA (rHSA) is essential as a safer and potentially unlimited alternative to pHSA.

Over the past decades, various expression systems have been used to produce rHSA, including *Escherichia coli* (13), *Saccharomyces cerevisiae* (14), *Kluyveromyces lactis* (15), *Pichia pastoris* (16), transgenic animals (17), and transgenic plants (18–21). Attempts to produce rHSA in tobacco leaves and potato tubers achieved expression levels of 0.02% of total soluble protein (TSP) (18), and expression was increased to 0.2% of TSP by targeting the rHSA to the apoplast of potato tubers (19). Recently, an expression level of 11.1% of TSP was obtained by expressing

rHSA in tobacco leaf chloroplasts (20). More recently, an rHSA expression level of 11.5% of total proteins was achieved in a rice cell culture by a sugar starvation-induced promoter (21). Although rHSA has been successfully expressed in these systems, none of them has proven to be cost-effective at large scale.

Plant seeds, especially cereal crop seeds, are promising vehicles for producing recombinant proteins, because they can achieve high accumulation of recombinant protein, display high levels of protein stability, stored for long periods of time, and are well controlled on a production scale (22, 23). Human lysozyme and lactoferrin produced for oral administration have been successfully expressed in rice seeds (24, 25). Here, Healthgen developed rice seeds as a bioreactor for large-scale production of *Oryza sativa* recombinant HSA (OsrHSA). OsrHSA can be highly and stably expressed in rice seeds and can be processed cost-effectively. OsrHSA was found to be equivalent to pHSA in terms of biochemical properties, physical structure, functions, and immunogenicity.

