## **2.3 In summary, the risk/benefit balance is considered acceptable to administer OsrHSA to healthy volunteers. Preclinical Studies**

### **2.3.1 Non-clinical Pharmacology**

The nonclinical pharmacology program for OsrHSA has been designed to evaluate the *in vivo* efficacy, immunopharmacological activity and safety profiles in animals to predict the pharmacologic profile of OsrHSA in human. The *in vivo* efficacy of OsrHSA was evaluated in the treatment of ascites of high-fat diet induced hepatic cirrhosis in a Wistar rat model, as well as in hemorrhagic shock model using male Japanese rabbits. Similar efficacy of OsrHSA and HpHSA has been demonstrated in these two animal disease models.

The effects of OsrHSA on the immune function of mammalian systems were investigated in three studies. No active systemic anaphylaxis (ASA) reaction was induced in rabbits, after primed with OsrHSA/CFA and challenged with OsrHSA/IFA, with no elevated total IgG, IgM, IgA, IgE production detected. No passive cutaneous anaphylaxis (PCA) induced in the guinea pigs after transfer the sensitized serum from the rabbits. 1/1436 and 0/200 anti-HCP IgE antibody was detected in a preliminary non GLP study and an US-GLP study, suggesting a low risk of the HCP from *Oryza sativa* in inducing allergic responses in humans. T-cell mediated DTH study confirmed that OsrHSA and HpHSA were weakly immunogenic in soluble forms as a foreign antigen to mice. If administered as soluble proteins, OsrHSA was unable to induce DTH response in mice, which suggested a low risk of inducing type IV hypersensitivity in human subjects.

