A full battery of study was conducted to evaluate the genotoxicity of OsrHSA as required in ICH S2 (R1) on Genotoxicity testing and Data Interpretation for Pharmaceuticals Intended for Human Use, June 2012. Ames test, chromosomal aberration test as well as *in vivo* micronucleus study confirmed that OsrHSA has no potential genotoxicity.

Host cell protein (HCP) is the main impurity in the formulations of OsrHSA. The potential toxicity and immunogenicity induced by HCP was evaluated in a 2-week daily repeat *i.v.* dose non-GLP study in SD rats. No clinical findings were observed for 25 µg/kg HCP, that is equivalent to the possible HCP presented in 5 g/kg OsrHSA.

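### Exclusion 16 joins rice IgE and rice IgG with *and*, so read literally it admits a volunteer who is positive for rice IgE alone and has no allergy history

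*Combined protocol and SAP*

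**What the plan says.** The lead-in to section 5.3 is "Subjects who meet any of the following criteria cannot be enrolled". Item 16 in that list is "Positive Ig E and Ig G against rice at screening". Item 4 is the other exclusion that names rice. It begins "Subjects who have any history of allergy to food or drug will be excluded" and adds in brackets "Including allergies, hypersensitivity, or intolerance to rice or rice products". Item 20 is a general clause: "Any reason which, in the opinion of the Qualified Investigator, would prevent the subject from participating in the study".

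On the product, section 2.1 says "OsrHSA can be highly and stably expressed in rice seeds and can be processed cost-effectively", and section 2.3.3 says "Host cell protein (HCP) is the main impurity in the formulations of OsrHSA". Section 2.3.1 reports that "1/1436 and 0/200 anti-HCP IgE antibody was detected in a preliminary non GLP study and an US-GLP study" and concludes from this that rice host cell protein carries a low risk of allergic response in humans.

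The schedule of activities (Table 1) has a single row for rice IgE and IgG, which includes screening. The row carries no decision rule, and no section defines a positive result for either assay.

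**The concern.** Item 16 is a safety-related entry criterion for a product of rice origin, tested in healthy volunteers who gain nothing from treatment. A serology criterion adds to a history criterion because it can find a volunteer who is sensitised but has never had a recognised reaction. On its literal reading, item 16 lets that volunteer through whenever IgG is negative.

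There is also a question of consistency. If two screeners can take the same IgE-positive, IgG-negative report and reach opposite enrolment decisions, both in good faith, the enrolled population is not fixed by the protocol. Section 8.2 allows no authorised deviations, so the criteria have to work as printed.

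**Working it through.** No sample size, power or error rate is involved, so the check is a truth table followed by a search for any other rule that would close the gap.

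**Step 1: how the criteria combine.** The lead-in makes any one numbered item sufficient to exclude. It acts between items and does not split the conjunction inside item 16.

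**Step 2: item 16 under its two readings.**

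| Rice IgE | Rice IgG | Literal *and* | Read as *either* |
|---|---|---|---|
| + | + | excluded | excluded |
| + | − | not excluded | excluded |
| − | + | not excluded | excluded |
| − | − | not excluded | not excluded |

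The readings differ in the two single-positive rows.

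**Step 3: does another criterion catch the IgE-only volunteer?**

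- Item 4 depends on a history of allergy, hypersensitivity or intolerance. It does not reach a sensitised volunteer without such a history.
- Item 10 also depends on history, and concerns components of plasma-derived albumin.
- Inclusion criterion 4 (section 5.2) asks for a general judgement of good health from history, examination and screening tests. It gives no rule on rice antibodies.
- Item 20 permits a discretionary exclusion but does not require one.
- The Table 1 row orders the test and attaches no consequence to the result.

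None of these is a stated rule that excludes on rice IgE alone.

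**Step 4: what drafting practice in the list suggests.** Item 13 joins two hepatitis infections with *or*, and item 19 joins three screening tests with *or*. In both, one positive is enough. Set against these, *and* in item 16 looks deliberate. But item 12 lists four anatomical sites of obstructive disease joined by *and*, where obstruction in any one must be meant. Set against that, *and* in item 16 could be a loose list. Usage in the section does not settle the matter.

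**Step 5: fit with the protocol's own risk argument.** For host cell protein, section 2.3.1 infers low allergic risk from IgE findings and attaches no IgG condition. An entry rule that acts on IgE only when IgG is also positive does not follow that reasoning.

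**Step 6: size.** Let *a* be the screened fraction positive on both tests, *b* the fraction positive on IgE only, and *c* the fraction positive on IgG only. Item 16 then excludes:

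- literal reading: *a*
- IgE positive regardless of IgG: *a* + *b*
- either result: *a* + *b* + *c*

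Compared with the literal reading, the additional screen failures are *b*, or *b* + *c* if IgG alone also excludes. The documents give no value for *a*, *b* or *c*. The nearest figure is the anti-HCP IgE count, 1/1436 = 0.07% in the non-GLP study and 0/200 in the GLP study. That is an assay for host cell protein antibody, and section 2.3.1 does not describe who was sampled. It cannot stand in for the prevalence of rice IgE in this population.

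**The case against.** The strongest reply is that item 16 is merely loosely drafted. On this view it names two disqualifying results, as item 12 names several organs, and any sensible site would exclude on either. This has force. A reader might infer from the text that the plan requires both antibodies and means to admit IgE-positive volunteers. The documents do not support that, because the list's use of *and* is not consistent. What the reply cannot do is make the criterion clear. It shows that two readings are available, and items 13 and 19 show that the authors wrote *or* elsewhere when one positive was enough.

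A second reply is that the gap is narrow. Item 4 already removes anyone with known rice allergy or intolerance, and indeed any food or drug allergy history. Item 20 lets the investigator remove others. This stands as a limit on size: what remains is an IgE-positive, IgG-negative volunteer with no such history whom the investigator does not choose to exclude. But discretion is not a rule, and such a volunteer is the one a serology criterion is best placed to find.

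A third reply is that nothing in the documents justifies excluding on IgG alone. That is correct. The allergic-risk argument supports acting on IgE and does not extend to an isolated IgG result.

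**Conclusion.** The point holds as a defect of wording with a literal gap. As printed, item 16 can be followed exactly and still admit a volunteer positive for rice IgE alone, and no other mandatory criterion prevents it by rule. Because this is a safety entry criterion and the correction is nearly free, it should be corrected and not left to site interpretation. The number of volunteers affected is unknown and may be small. The clinical relevance assumes that the rice IgE assay detects proteins related to the residual host cell protein, which the documents do not describe.

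Four stronger conclusions might be drawn and are not supported:

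- *Items 4 and 16 conflict.* They do not. One is about history and the other about serology, and under the lead-in they add to each other.
- *One hypersensitivity reaction would halt escalation.* Under section 4.2.3 it stops dosing for that individual. Under section 4.2.4 escalation is held when at least 2 subjects in a cohort meet the subject stopping rules, when at least 2 of 8 have Grade 3 or higher toxicity, or for an SAE not obviously unrelated. A single non-serious reaction does not meet these.
- *The post-dose rice antibody results would be compromised.* Rice IgE and IgG are not named endpoints in section 3.2 and have no planned comparison in section 11.4.3. Table 1 provides a screening value to compare against.
- *A percentage of screened volunteers can be put on the difference between readings.* Any such figure would rest on prevalences that the documents do not give.

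**What to change.** Reword item 16 so that it states the effect of each result pattern, and in particular of each single-positive result:

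- State the consequence of a positive rice IgE with a negative IgG explicitly, so that such a volunteer is not admitted merely through the conjunction.
- State separately whether a positive rice IgG with a negative IgE excludes. This is for the sponsor's clinicians to decide, since the documents give no basis either way.
- Define a positive result for each assay.
- Reconcile the final wording with the IgE-based risk argument in section 2.3.1.

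The cost is a short amendment to one criterion and some additional screen failures: *b* in the notation above, or *b* + *c* if IgG alone excludes. Neither can be computed from the documents. The second could be noticeably larger, so the sponsor should look at any rice IgG prevalence data it holds before choosing that option. Sample size and analysis are unaffected.

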#### **5.4 Meals and Dietary Restrictions**

Subjects will receive a standard diet whilst resident in the clinical center. For standardization purpose, the study drug infusion will start at least 30 minutes after subjects have been served a

light breakfast. No food will be allowed until at least 1 hour after the end of infusion. Standardized meals will be served at appropriate times thereafter.

Water will be provided *ad libitum* at all times.

In addition, subjects will be required to abstain from:

- food containing poppy seeds within 24 hours prior to admission;
- food or beverages containing xanthine derivatives or xanthine-related compounds (coffee, black/green tea, chocolate) or energy drinks from 48 hours prior dosing until EOS;
- dietary supplements within 1 week prior to study drug administration until EOS, unless, in the opinion of the Investigator and Sponsor, the dietary supplement will not interfere with the study;

### **5.5 Tobacco, Alcohol and Illicit Drugs**

Refrain from intake of alcoholic beverages from 72 hours prior to study treatment administration until Day 8 postdose. After Day 8, subjects are discouraged from consuming alcohol until the completion of the study, but may consume no more than 1 unit of alcohol per day.

Subjects will be required to abstain from using nicotine products, or soft or hard drugs from screening and throughout the study.

### **5.6 Medication**

Use of any prescription, herbal supplements, or nonprescription drugs will be prohibited within 1 month or 5 half-lives (whichever is longer) prior to study drug administration and until EOS, unless, in the opinion of the Investigator and Sponsor, the medication will not interfere with the study. No concomitant drug therapy will be allowed during the study except one(s) required for the medical management of an adverse event.

Any concomitant medication use other than the occasional use of acetaminophen will be evaluated on a case-by-case basis by the Principal Investigator or a physician. The use of hormonal contraceptives will be allowed and documented. All concomitant medication use will be documented.

### **5.7 Activity**

Subjects should refrain from strenuous exercise for 48 hours before admission to the clinical center and throughout the study. Subjects may participate in light recreational activities during the study (eg, watching television, reading).

Subjects will be advised not to donate blood or plasma from at least 12 weeks before study drug administration and for at least 3 months after the last dose administration.

For safety reasons, subjects will be required to remain semi-reclined and avoid lying down or sleeping for the first 4 hours after the end of study drug infusion. However, failure of subjects to comply with these requirements does not constitute a deviation from the protocol if it is medically necessary, procedurally required, or to go to the bathroom. When appropriate, subjects will be accompanied by a staff member during ambulation.

## **5.8 Randomization and blinding**

Subjects in the clinical site will be 6:2 randomized to receive either the study product or placebo prior to dosing, the randomization code will not be available to the Bioanalytical Division until the clinical and analytical phases have been completed for each cohort.

Both the principal investigator and subjects will be blinded as to whether a subject is receiving study product, or placebo. A designated person in the Investigational Pharmacy will dispense the appropriate drug accordingly. The Safety Review Committee can request unblinded randomization scheme in order to evaluate the data.

Each bottle administered to subjects will have a unique code, and quick unblinding will be performed by Investigational Drug Pharmacy, the principal investigator, or the sponsor, should a medical emergency arise for a participant.

Upon completion of the study participation, all subjects will be unblinded

## **6 STUDY INTERVENTION**

### **6.1 Study Drug Description**

OsrHSA drug product is presented as a slightly viscous, yellow to brownish clear liquid packed in Type I neutral borosilicate moulded glass vial capped with chlorobutyl rubber stopper with Polytetrafluoroethylene (PTFE)/Polyhexafluoroethylene film and plastic-aluminum seal. Each vial contains 10 g OsrHSA protein, 0.261 g sodium octanoate, 0.409 g sodium chloride, pH6.4~7.4. The total volume is 50 ml.

Normal Saline (0.9% Sodium Chloride) will be used as the placebo.

### **6.2 Study Drug Packaging and Labeling**

OsrHSA drug product is packed in Type I neutral borosilicate moulded glass vial capped with chlorobutyl rubber stopper with Polytetrafluoroethylene (PTFE)/Polyhexafluoroethylene film and plastic-aluminum seal. There will be a carton package. The labels for carton and vial are shown below.

Recombinant human serum albumin from *Oryza sativa* (OsrHSA). 20% solution with 10g of drug.

#### **6.2.1 Drug Storage and Handling**

OsrHSA drug product is stored at 2-8°C, protected from light. At time of use, the drug product vial is directly connected to the infusion line equipped with a 0.2µm in-line filter and administered via IV infusion.

#### **6.2.2 Study Drug Compliance and Accountability**

The site should record and maintain shipping and receiving records of the study drug, and report to the Sponsor immediately any defect or issues with quality, quantity or interruption in cold-chain shipping.

The site will maintain accurate dosage preparation records and should ensure that all pertinent/required information on the preparation and administration of the dose is captured in source documents, and appropriate dosing information is entered onto eCRFs. Such information should be made available to the Sponsor's site monitoring representative(s) during monitoring visits.

#### **6.2.3 Disposal and Destruction**

Upon termination of the study, or at the request of the sponsor, the pharmacist (or designee) must return the study drugs to Sponsor, unless it is destroyed at the clinical site as agreed upon by both the sponsor and the clinical site.

#### **6.2.4 Treatment Allocation and Administration, Dosing Regimen**

This is a Phase 1 randomized, double blinded, placebo-controlled study. Subjects will be randomized. Both subjects and investigator will be blinded.

[figure not shown]
1. Parenteral drug products should be prepared by using appropriate aseptic technique, and inspected visually for particulate matter and discoloration prior to administration, whenever solution and container permit.

2. Treatment Allocation and Administration: OsrHSA will be diluted with normal saline to a total volume of 200ml.

The total infusion time will be 2hr ± 20min.

The OsrHSA infusion rate is lower than 2ml/min. The procedures used for administration are following:

- First, set up intravenous channel and intravenous injection of 50 ml saline. The infusion rate for normal saline will be 5ml/min.
- Second, OsrHSA or placebo will be administered via an infusion line equipped with a 0.2µm in-line filter. And monitor for infusion-related AEs during administration. The rate of intravenous should be lower than 2 ml/ min and cautions should be taken. Dose interruption based on intolerability will be captured in the monitoring of infusion start and stop times.
- Third, flush with 50ml normal Saline after the dose. The infusion rate for normal saline will be 5ml/min.

All dose administrations will be performed in the clinical center under the supervision of appropriately trained staff.

Further detailed instructions on handling and administration of study drug is described in the separate Pharmacy Manual.

